Reproductive Toxicity	
Non-Clinical Data: In the rat embryofetal development study, there were no maternal or developmental toxicity at doses ≤ 200 mg/kg/day. There were maternal and developmental toxicity at dose of 450 mg/kg/day.
 
In the rabbit embryofetal development study, GSK2982772 was administered at doses of 0, 10, 100, 300 or 600 mg/kg/day on gestation day 7 to 19. No developmental toxicity was evident at doses up to 300 mg/kg/day. There was maternal toxicity at dose of ≥ 300 mg/kg/day and no tolerability at dose of 600 mg/kg/day.
	
Subject Selection:
 
 Males will be included in this study only if they agree to use highly effective methods of contraception and avoid conception until last visit. 
Withdrawal Criteria:
 
 If a female partner should become pregnant during the study, study medication should be discontinued. She will be followed to determine the outcome of the pregnancy.
Drug Interaction	
Non-Clinical Data: In vitro studies with GSK2982772 assessing potential drug-drug interactions with Cytochrome P450 3A4 (CYP3A4) substrates and P-glycoprotein (P-gp) inhibitors were completed. To date, formal drug interaction studies in humans have not been performed with GSK2982772. There is a low risk that GSK2982772 could be an inducer of CYP3A4 and therefore may lower circulating levels of concomitant medications that are metabolised by CYP3A4 when co-administered with GSK2982772. GSK2982772 is a P-gp substrate and therefore co-administration with concomitant medications that are P-gp inhibitors could increase circulating levels of GSK2982772. There is a low risk that GSK2982772 could be a perpetrator of organic anion transporter 3 (OAT3) substrates. Methotrexate (MTX) is an OAT3 substrate in which GSK2982772 could potentially impair the clearance of MTX. See Section 4.3.6 of GSK2982772 IB [GlaxoSmithKline Document Number 2014N204126_04].
	
Subject Selection:
 
 Subjects who are taking concomitant medications known to inhibit P-gp or CYP3A4 will be excluded from the study. 
Subject Monitoring:
 
 Subjects' concomitant medication usage will be reviewed prior to inclusion and monitored throughout the study. Subjects should be monitored throughout the study for potential effects of interaction between GSK2982772 and other concomitant medications.

3.3.2. Benefit Assessment

This study is being conducted in healthy participant with no significant medical history. Subjects will not receive benefit from this study. However, knowledge from this study may contribute to the development of GSK2982772 and may benefit patients in the future.

3.3.3. Overall Benefit: Risk Conclusion

It is considered acceptable to conduct this study in healthy subjects, because whilst they will receive no direct medical benefit, the risks from the study treatment and procedures are minimal. The study will be conducted in a fully equipped clinical pharmacology unit with access to hospital emergency facilities.

Taking into account the measures taken to minimize risk to subjects participating in this study, the potential risks identified in association with GSK2982772 are justified by the anticipated benefits that may be afforded by the future development of a new therapy in an area of unmet need.

4. OBJECTIVES AND ENDPOINTS

Objectives	Endpoints
To assess the safety and tolerability of TID doses for one day of GSK2982772 in Japanese healthy male subjects	Adverse events (AEs) Change in laboratory values (clinical chemistry, haematology and urinalysis), 12-lead ECG and cardiac telemetry, vital signs (blood pressure, pulse rate, and body temperature) Physical examinations, including neurological examinations
To characterise the PK profile of TID doses for one day of GSK2982772 in Japanese healthy male subjects	Derived PK parameters for GSK2982772, including area under the plasma drug concentration versus time curve over 24 hr (AUC(0-24)) and AUC over each dose interval (i.e. AUC(0-7), AUC(7-14) and AUC(14-24)), maximum observed plasma drug concentration (C _{max}) following each dose, time to maximum observed plasma drug concentration (T _{max}) following each dose, terminal half-life (t _{1/2}) following the third dose, observed trough plasma drug concentrations (C ₀ , C ₇ , C ₁₄ and C ₂₄), where data allow

5. STUDY DESIGN

5.1. Overall Design

This study will be a double-blind with respect to subjects, investigators and site staff (with the exception of the unblinded site pharmacist), TID oral doses for one day,

ascending dose, randomized, placebo-controlled, 4-way crossover study, shown as the table below;

Group	N	Period 1	Period 2	Period 3	Period 4
A	3	Placebo, TID	60 mg, TID	120 mg, TID	240 mg, TID
B	3	60 mg, TID	Placebo, TID	120 mg, TID	240 mg, TID
C	3	60 mg, TID	120 mg, TID	Placebo, TID	240 mg, TID
D	3	60 mg, TID	120 mg, TID	240 mg, TID	Placebo, TID

Treatment Groups and Duration:

Screening	Within 30 days prior to the first dose on Day1.
Treatment Period	
The study will be comprised of four study periods each at least 7 days in duration with subjects in-house for 4 nights (through 72 hrs after the first dose). During each treatment period, subjects will be admitted to the unit the day before dosing and will be discharged after completion of the 72 hrs post-dose assessments.
 
Each subject will receive oral TID doses of GSK2982772 in each treatment period. For TID dosing, GSK2982772 or placebo will be administered at 0 hr (the first dosing), 7 hr (the second dosing) and 14 hr (the third dosing) on Day 1 in each period. On Day 1, subjects will fast 8hr overnight prior to first dose. A breakfast will be served approximately 2hr after first dose. Lunch and dinner will be served between 2 to 3hr prior to second and third doses, respectively.

Washout Period	Will be at least 7 days between treatment period doses for an individual subject.
Follow-up	At least 7 days, and no greater than 14 days after last study treatment administration. If warranted, additional follow-up visits may be scheduled.

5.2. Number of Subjects

Sufficient Japanese healthy male subjects will be enrolled such that up to 12 subjects complete dosing and critical assessments.

If subjects prematurely discontinue the study, additional replacement subjects may be randomized in order to guarantee that sufficient subjects are treated with GSK2982772 at any given dose before escalating to the following dose. Replacement subjects will be assigned to the same treatment sequence and start from the period to be replaced at the discretion of the GSK and in consultation with the principal investigator.

5.3. Sentinel Dosing

The doses will be staggered such that for each dose, on Day 1 of Period 1, 2 and 3, two of the 12 subjects will be randomized to treatment (one subject will receive GSK2982772 and one subject will receive matched-placebo). Assuming 2 subjects are dosed on Day 1 and assuming adequate safety (AEs, clinical labs, vital signs, 12-Lead ECGs and findings during continuous cardiac telemetry) in the blind judgment of the principal investigator

and GSK Medical Monitor through at least 24 hrs after their third dose on Day 1, the remaining subjects may be randomized to dosing in that period.

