2: Follow-up Visit to occur at least 7 days, and no greater than 14 days after last study treatment administration. If a participant withdrew from the study after received GSK2982772 or placebo dose, the safety assessments listed at follow-up visit will be required.

Detailed Time and Events Table for Days 1-4 (common Period1-4)

Procedure ¹	Day -1	Day 1																									
		Pre-dose	0	20 min	40 min	1 hr	1.5 hr	2 hr	3 hr	4 hr	5 hr	7 hr	7 hr 20 min	7 hr 40 min	8 hr	8.5 hr	9 hr	10 hr	11 hr	12 hr	14 hr	14 hr 20 min	14 hr 40 min	15 hr	15.5 hr		
Admission	X																										
Physical Examination	X	X						X				X ⁶													X ⁶		
Hema/Chem/Urinalysis tests	X																										
Vital signs ²		X						X				X ⁶												X ⁶			
12-lead ECG		X						X				X ⁶											X ⁶				
Cardiac telemetry ³		<=====																									
PK blood sampling		X		X	X	X	X	X	X		X	X ⁷	X	X	X	X	X	X	X		X	X ⁷	X	X	X	X	X
Neurological Examination	X							X																X ⁸			
Study Treatment			X									X											X				
Pharmacogenetic Sampling (PGx) ⁴		<=====																									
Meals Served	X							X ⁹			X ⁹											X ⁹					
AE Review ⁵		<=====																									
Concomitant Medication Review		<=====																									
Discharge																											

Procedure ¹	Day 2								Day 3		Day 4
	16 hr	17 hr	19 hr	22 hr	24 hr	28 hr	32 hr	36 hr	48 hr	60 hr	72 hr
Admission											
Physical Examination					X			X	X		X
Hema/Chem/Urinalysis tests											X
Vital signs ²					X				X		X
12-lead ECG					X				X		X
Cardiac telemetry ³	=====>										
PK blood sampling	X	X	X	X	X	X	X	X	X	X	X
Neurological Examination					X				X		X
Study Treatment											
Pharmacogenetic Sampling (PGx) ⁴	=====>										
Meals Served						X ¹⁰		X ¹⁰	X ¹⁰	X ¹⁰	
AE Review ⁵	=====>										
Concomitant Medication Review	=====>										
Discharge											X

1: In this study, baseline is Day -1 and Day 1 pre-dose tests.

2: Vital signs include PR, BPs and temperature.

3: Only 24 hrs following the first dose administration

4: A PGx blood sample will be collected at any time during the study after randomization and provided informed consent for genetic reserch. The participation is optional for each subject.

5: All SAEs will be collected from the signing of the ICF until the follow-up visit at the time points specified. All AEs will be collected from the start of treatment until the follow-up visit at the time points specified.

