6.3. Lifestyle Restrictions

6.3.1. Meals and Dietary Restrictions

Refrain from consumption of red wine, Seville oranges, grapefruit or grapefruit juice, pomelos, citrus fruits, grapefruit hybrids, or fruit juices from 7 days prior to the start of study treatment until follow-up visit.

Once in the clinical unit subjects will not be allowed to eat anything other than the food provided by the study centre.

- Subjects must then fast from all food and drink (except water) for 8 hrs prior to first dose.
- Subjects must then fast from all food and drink (except water) for 8 hrs prior to any clinical laboratory evaluations.
- Water is permitted with dosing and at all times except 1 hr pre-dose through 2 hrs post-dose.
- On Day 1, breakfast will be served approximately 2 hr after first dose. Lunch will be served between 2 to 3 hr prior to second dose. Dinner will be served between 2 to 3 hr prior to third dose. On Day 2-3, meal will be served per unit schedule. Mealtime will be described in SRM.

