9. STUDY ASSESSMENTS AND PROCEDURES

- Study procedures and their timing are summarized in the SoA.
- Protocol waivers or exemptions are not allowed.
- Immediate safety concerns should be discussed with the GSK immediately upon occurrence or awareness to determine if the participant should continue or discontinue study treatment.
- Adherence to the study design requirements, including those specified in the SoA, is essential and required for study conduct.
- All screening evaluations must be completed and reviewed to confirm that potential participants meet all eligibility criteria. The principal investigator will maintain a screening log to record details of all participants screened and to confirm eligibility or record reasons for screening failure, as applicable.
- The maximum amount of blood collected from each participant over the duration of the study, including any extra assessments that may be required, will not exceed 400 mL.
- Repeat or unscheduled samples may be taken for safety reasons or for technical issues with the samples.

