12.2. Appendix 2: Clinical Laboratory Tests

- The tests detailed in Table 1 will be performed by the local laboratory.
- Protocol-specific requirements for inclusion or exclusion of participants are detailed in Section 6 of the protocol.
- Additional tests may be performed at any time during the study as determined necessary by the investigator or required by local regulations.

Table 1 Protocol-Required Safety Laboratory Assessments

Laboratory Assessments	Parameters			
Hematology	Platelet Count	RBC Indices: MCV MCH %Reticulocytes	WBC count with Differential: Neutrophils Lymphocytes Monocytes Eosinophils Basophils	
	RBC Count			
	Hemoglobin			
	Hematocrit			
Clinical Chemistry ¹	BUN	Potassium	Aspartate Aminotransferase (AST)	Total and direct bilirubin
	Creatinine	Sodium	Alanine Aminotransferase (ALT)	Total Protein
	Glucose (fasting)	Calcium	Alkaline phosphatase	Albumin
	Uric acid	TG	Total Cholesterol	LDL-cholesterol
	HDL-cholesterol	LDH	GGT	CK (CPK)
	Amylase	Chloride	Phosphorus	CRP
Routine Urinalysis	
 • Specific gravity • pH, glucose, protein, blood, ketones, bilirubin, urobilinogen by dipstick • Microscopic examination (if blood or protein is abnormal) 			
Other Screening Tests	
 • Urine drug screen (to include at minimum: Phencyclidines [PCP], Benzodiazepines [BZO], Cocaine [COC], Amphetamines [AMP], Tetrahydrocannabinol [THC], Opiates [OPI], Barbiturates [BAR], Tricyclic antidepressants [TCA]) • Serology (Syphilis [RPR & TP], TB, HIV antigen/antibody, HTLV-1 antibody, hepatitis B surface antigen [HBsAg], and hepatitis C virus antibody) 			

NOTES :

1. Details of liver chemistry stopping criteria and required actions and follow-up assessments after liver stopping or monitoring event are given in Section 8.1 and Appendix 7. All events of ALT $\geq 3 \times$ upper limit of normal (ULN) and bilirubin $\geq 2 \times$ ULN ($> 35\%$ direct bilirubin) or ALT $\geq 3 \times$ ULN and international normalized ratio (INR) > 1.5 , if INR measured, which may indicate severe liver injury (possible Hy's Law), must be reported as an SAE (excluding studies of hepatic impairment or cirrhosis).

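### Sentinel release is permitted from 38 hr and depends on clinical labs, but no post-dose labs are scheduled before 72 hr and Protocol 5.3 does not say how to close the gap

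*Protocol*

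**What the plan says.** Protocol 5.3 (repeated in the Synopsis) doses two sentinels first in Periods 1 to 3, one on GSK2982772 and one on placebo. The others follow "assuming adequate safety (AEs, clinical labs, vital signs, 12-Lead ECGs and findings during continuous cardiac telemetry") in the blinded view of the principal investigator and the Medical Monitor. The time condition is "through at least 24 hrs after their third dose on Day 1, the remaining subjects may be randomized to dosing in that period".

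In the SoA (Protocol Section 2), the row "Hema/Chem/Urinalysis tests" is marked in each period only on Day -1, which is baseline, and at 72 hr. The SoA in SAP Appendix 2 agrees. Protocol 9.3.5 leaves lab timing to the SoA.

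Earlier labs are allowed but optional. Section 9 says "Repeat or unscheduled samples may be taken for safety reasons or for technical issues with the samples", and Appendix 2 says "Additional tests may be performed at any time during the study as determined necessary by the investigator".

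The separate dose-escalation review in 5.4 covers data up to Day 4, so it includes the 72-hr labs.

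SAP 2.3 restates the sentinel rule with the second dose in place of the third.

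**The concern.** Protocol 5.6 presents sentinel dosing as part of the cautious approach for the first exposure of Japanese subjects, and 5.3 names labs as one of five data types behind the release decision. A site that runs the SoA as written will hold no post-dose lab result when release first becomes permissible.

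Reviewers could then act in two ways. They could apply the lab condition strictly and order an unplanned draw or wait. Or they could judge safety on the data in hand. In the second case, a lab change in the active sentinel would first be seen after the others at that dose level had been dosed. ALT, on which the liver stopping rule in Appendix 7 depends, can be seen only in a lab result.

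**Working it through.** **Release floor.** The third dose is at 14 hr (Protocol 5.1), so the floor is 14 + 24 = 38 hr.

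**Practical start.** The first dose follows an overnight fast (Protocol 5.1), and SAP 8.1.5.1 calls it the morning dose. No clock time is given. If the first dose is between 06:00 and 10:00, 38 hr falls between 20:00 on Day 2 and midnight. The next practical start is therefore the following morning, about 48 hr. This is an inference; no document states it.

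**Scheduled sentinel data (Protocol SoA; AE review is continuous).**

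| Time | Due |
|---|---|
| 24 hr | Vital signs, ECG, physical and neurological examinations; telemetry ends |
| 36 hr | Physical examination |
| 38 hr | Release floor; no safety assessment due |
| 48 hr | Vital signs, ECG, physical and neurological examinations |
| 72 hr | As at 48 hr, plus the first post-dose labs |

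The telemetry window is "Only 24 hrs following the first dose administration".

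**Gap to the first scheduled post-dose labs.** From the floor, 72 - 38 = 34 hr. From a 48-hr start, 72 - 48 = 24 hr. With that start, the remaining subjects' third dose is at 48 + 14 = 62 hr, which is 72 - 62 = 10 hr before the sentinels' labs.

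**Subjects affected.** The groups have 3 subjects each, and SAP 2.3 gives the sentinel doses as 60, 120 and 240 mg in Periods 1, 2 and 3. One active sentinel is subtracted in each period.

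- Period 1, 60 mg (groups B, C, D): 9 - 1 = 8
- Period 2, 120 mg (C, D): 6 - 1 = 5
- Period 3, 240 mg (D): 3 - 1 = 2

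The total is 8 + 5 + 2 = 15 of 9 + 6 + 3 = 18 new-dose exposures.

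**Fasting.** Protocol 6.3.1 states: "Subjects must then fast from all food and drink (except water) for 8 hrs prior to any clinical laboratory evaluations". The last meal mark before 38 hr is at 36 hr in the protocol SoA and 32 hr in the SAP SoA. That leaves 2 or 6 hr, so a draw at the floor would nominally break the fast. At 48 hr the interval is 12 or 16 hr if the sample precedes the 48-hr meal. At 72 hr it is 72 - 60 = 12 hr in both. These times are nominal, because Day 2 and 3 meals follow the unit schedule in the Study Reference Manual.

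**Delay, assuming morning starts and same-day results.**

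- Release on the 72-hr labs: start at 96 hr; 96 - 48 = 48 hr, or 2 days per period and 6 days over three periods.
- Release on a 48-hr panel: start at 72 hr; 72 - 48 = 24 hr, or 1 day per period and 3 days in total.

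**Blood volume against the 400 mL limit (Protocol Section 9).**

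- PK: 32 to 34 samples per period (the SoA row is broken in the available text) x 2 mL x 4 periods = 256 to 272 mL.
- Lab draws: screening 1 + Day -1 x 4 + 72 hr x 4 + follow-up 1 = 10. Volume per draw is not stated; 8 to 12 mL is assumed, giving 80 to 120 mL.
- Optional genetic sample: 6 mL.
- Total as planned: 256 + 80 + 6 = 342 to 272 + 120 + 6 = 398 mL.
- With one added draw: 342 + 8 = 350 to 398 + 12 = 410 mL.

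Any separate blood for screening serology and the tuberculosis test comes on top.

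**The case against.** The strongest reply is that 5.3 already protects these subjects. Labs are a named condition, the 24 hr is a minimum, and release is permissive. Lab safety cannot be judged without a post-dose result, so the text implies a draw or a wait. The protocol authorises the draw, bars waivers, and places testing on site: "The tests detailed in Table 1 will be performed by the local laboratory". This stands, and it reduces the point to an undefined step in the release rule. It does not remove it, because the schedule provides no result at the stated floor and no sentence names the missing one.

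The risk is also low. The 60 mg TID level is 3 x 60 = 180 mg/day, below the 2 x 120 = 240 mg/day given for 14 days in Study 200975, where Protocol 5.7 reports no clinically significant lab pattern. One-day 120 and 240 mg TID were completed and tolerated in non-Japanese subjects (Protocol 3.2). The count of 15 therefore mixes unequal exposures and should not be read as 15 subjects at material risk.

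A reader might infer three stronger things that the documents do not support:

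- **That the protocol authorises release without labs.** It does not; it lists them as a condition.
- **That the other sentinel data are missing too.** Telemetry covers the first 24 hr, and by 48 hr new vital signs, ECG and examinations are due. At that start the gap is the labs.
- **That a higher dose could be reached without labs.** The escalation review in 5.4 includes Day 4 data. That review guards the next dose level, however, while sentinel dosing guards the remaining subjects at the same level.

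**Conclusion.** The point holds as a mismatch between the release rule and the schedule. The earliest permitted release is 38 hr, the first scheduled post-dose labs are at 72 hr, and the text does not say whether to draw early or to wait. The size is a 34-hr gap at the floor, or 24 hr at a 48-hr start, with up to 15 of 18 new-dose exposures in Periods 1 to 3 falling before the sentinels' first post-dose labs if reviewers proceed without them.

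The 38-hr floor, the lab schedule and the counts follow directly from the documents. The 48-hr start, and every delay measured from it, is inferred from a morning first dose.

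The second-dose wording in SAP 2.3 would put release at 7 + 24 = 31 hr. A reader might take this as a competing rule. SAP 2.3 only summarises the protocol, and SAP 2.1 declares no change to the planned analysis, so it is best treated as an editorial slip.

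**What to change.** State in Protocol 5.3 and the Synopsis that the remaining subjects are released only after the principal investigator and the Medical Monitor have reviewed at least one post-dose haematology, chemistry and urinalysis panel from both sentinels.

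**Default: the existing 72-hr panel.** It costs one sentence in each place and no extra blood. Its downside is the delay of about 2 days per period. Periods are defined only by a 7-day minimum, so the design can accommodate it.

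**Option: a fasting sentinel panel at about 48 hr, taken before the meal.** This needs an SoA footnote and 2 x 3 = 6 panels, and halves the delay to about 1 day per period. It should be chosen only if the site confirms from its own tube volumes that each subject stays within 400 mL, since the upper end of the assumed range exceeds that limit even before screening serology and tuberculosis blood. Keeping to one added draw per subject also requires six different sentinels. This is possible (a placebo subject from A, B and C in turn, each paired with a different group D subject), but the protocol does not specify it.

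Under either choice, correct the second-dose wording in SAP 2.3 to match the final rule.

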5.4. Dose Escalation Decisions

The decision to proceed to the next dose level of GSK2982772 within the study will be made by principal investigator and GSK Medical Monitor per each dosing periods.

Dose escalation decisions will be based on blind data obtained from 6 or more subjects receiving GSK2982772 at the prior dose level. The review of the data set will consist at a minimum of: all AEs, clinical laboratory values, vital signs, 12-Lead ECG up to Day 4 (at discharge) and findings during continuous cardiac telemetry in the previous dose (Section 8.1.1.).

5.5. Participant and Study Completion

A participant is considered to have completed the study if he has completed all phases of the study including the last visit or the last scheduled procedure shown in the SoA.

The end of the study is defined as the date of the last visit of the last participant in the study.

5.6. Scientific Rationale for Study Design

This study will include a placebo control study, to allow for evaluation of AEs attributable to treatment versus those independent of treatment.

In Study 200975, 67 subjects were exposed to active treatment. GSK2982772 was well-tolerated, with no deaths or other non-fatal SAEs being reported. Sentinel dosing approach was taken in Study 200975, where two subjects receive placebo or GSK2982772 on Day 1 and the remaining subjects are dosed after safety evaluation at 24 hrs of preceding two subjects. Since this study is the first study in Japanese subjects, this study adopts a cautious approach including sentinel dosing and will include rigorous safety monitoring to confirm the safety profile prior to dose-escalation of single dose of the next dose strength, which was the same way taken in the past non-Japanese study.

In the 4 week repeat dose nonclinical toxicology studies, neurological related events (uncoordinated movement, irregular gait, trembling, hunched appearance and decreased activity) were observed in some rats and monkeys. On the other hand, in the 13 week repeat dose nonclinical toxicology studies in rats or monkeys, or in the 39 week repeat dose nonclinical toxicology study in monkeys, no neurological-related events were observed in rats or monkeys. There have been some reports of lethargy, abnormal dreams, and depressed mood in Study 200975 (See IB for GSK2982772 [GlaxoSmithKline Document Number 2014N204126_04]). This study includes neurological exams by considering these findings from Study 200975.

In the currently ongoing non-Japanese healthy volunteer study (Study 205184) being conducted in the United Kingdom (UK), several asymptomatic arhythmias were detected in 6 out of 25 subjects treated with GSK2982772 or placebo. The study was temporarily

put on hold by GSK to assess the totality of these events. A formal review by the GSK Internal Cardiac Safety Panel, inclusive of both internal and external cardiologists, determined that the arrhythmic events were not likely related to GSK2982772 administration based on the timing and random occurrences of the events, the heterogeneity of the arrhythmias, the length of cardiac monitoring being performed during the study, and no findings in preclinical studies. Subsequently, the protocol was amended to increase the number of placebo subjects to balance randomization between active and placebo to understand the background cardiac patterns of subjects who are enrolled compared to when on treatment. Approval to proceed with the study was received from Medicines and Healthcare products Regulatory Agency (MHRA) on 22 March 2018. Study 200975 and Study 205184 did include telemetry, while the cardiac events related to the study drug were not observed in non-Japanese subjects including Study 205184. Since this study is the first study in Japanese subjects, telemetry will be planned in this study.

GSK2982772 concentrations decline rapidly until about 12 hrs post-dose, with a $t_{1/2}$ of approximately 2 to 3 hrs. It, therefore, is considered sufficient to allow at least 7 days washout between dosing periods. Also, 7 days follow up after the last dose is considered to be sufficient for safety evaluation.

In the ongoing Study 205184, there are two TID dose regimens of 120 mg TID and 240 mg TID. This study plans also TID dose regimen, which allows to compare the PK between Japanese subjects and non-Japanese subjects in order to support dosing of GSK2982772 in Japanese patient population in the Phase 2b dose ranging studies.

